#### **1. Primary End Points:**

There are two aspects to the primary end points of the study and as follows:

- 1) To value the efficacies of LNG-IUS as fertility-preserving treatment for early EC and EAH by pathologic response. Pathologic response to medicine treatment is categorized as complete response (CR), partial response (PR), no change (NC), and progressive disease (PD). CR is defined as the absence of any hyperplastic or cancerous lesion. PR is defined as the residual lesion with degeneration and atrophy of endometrial glands. NC is defined as residual lesion without degeneration or atrophy of endometrial glands. PD is defined as the appearance of endometrial cancer for EAH and grade 2 (G2) or 3 for EC.
- 2) To compare the rate of pregnancy and alive baby delivery.

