**Comments:**

(1) The basic history collection includes detailed history of prior treatment; with or without contraindications of oral highly active progestogens: hypertension, diabetes (DM), liver function damage, thrombotic disease and so on; with or without reproductive endocrine disease: infertility, PCO syndrome, insulin resistance (IR), impaired fasting glucose (IFG) and so on; with or without any other system disease; surgical history, allergy history; family history especially for carcinomas.

(2) The basic endocrine examinations include sex hormone, anti mullerian hormone (AMH), and insulin release test (IRT) to rule out PCO syndrome, IR, IFG, and DM. Follow-up treatment will be provided when necessary.

(3) If the patients have abnormality in breast ultrasound, she needs to visit the Department of Breast Surgery to evaluate the risk of continuous progesterone treatment.

(4) Based on the inclusion and exclusion criteria of this study, the patients are allocated to one of the arms by central randomization with study site allocation. The arms and interventions and the probability of distribution are as follows:

1) If the patients does not have thromboembolism, liver dysfunction, hypertension, or diabetes, she will be assigned to one of the following two groups, with a probability of 50%, respectively: a) sequential oral medroxyprogesterone acetate (MPA) 500mg QD group; and b) LNG-IUS (Mirena®) group.

2) If the patients are diagnosed of thromboembolism, liver dysfunction, hypertension, or diabetes, she will be assigned to one of the following two groups, with a probability of 50%, respectively: a) intramuscular injection of leuporelin acetate microspheres (GnRH-a) + LNG-IUS group; and b) LNG-IUS (Mirena®) group.

(5) For the groups of oral highly active progestogens, medicine treatment should only be continued if the liver function is normal, which is evaluated by monthly tests.

(6) For the groups of LNG-IUS, the medical device needs to be replaced by a new one on every hysteroscopy to insure adequate drug release

(7) Endometrial tissue sampling for diagnosis should be performed by hysteroscopy every 3 months, and the histologic diagnoses of all specimens are made by two categorized pathologists.

[figure not shown]

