(9) For the groups of LNG-IUS, the medical device needs to be replaced by a new one on every hysteroscopy to insure adequate drug release

(10) Endometrial tissue sampling for diagnosis should be carried out by hysteroscopy every 3 months, and histologic diagnoses of all specimens are made by two categorized pathologists.

(11) After 6 months' continuous progestogen-based therapy, if the patient has PR/NC, progestogen-based therapy should be continued for one more cycle (3 months), and if the patient still has PR/NC, she will withdraw from this trial and undergo hysterectomy; if the patient has CR at the second or third endometrial evaluation, fertility treatment will be initiated immediately; and if the patient has documented progression on the biopsies at any time, the protocol treatments will be stopped and hysterectomy be recommended.

(12) The option of natural conception or assisted reproduction should be discussed with the fertility specialist in the reproduction center of our hospital; assisted reproduction is recommended if the patient 1) has history of infertility; 2) has risk factors of infertility such as PCO syndrome, obesity, diabetes, and lack of ovulation; or 3) suffers from failed pregnancies after 6 months of natural conception.

(13) If the patient succeeds in conceiving, she will receive professional prenatal examinations from the obstetrics specialist in our hospital.

(14) All the professors in the Department of Obstetrics and Reproductive Center of our hospital are on this research team.

(15) Long-term follow-up will proceed even after treatments are finished, and corresponding clinical treatments will be provided for patients with different conditions.

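### The plan does not provide for masked or independent histology reading of the primary response, although treatment is open in practice

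*Combined protocol and SAP*

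**What the plan says.** **Endpoint.** Section I.1 (Primary End Points) makes pathologic response the first primary aspect. The categories are verbal:

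- Complete response (CR): "CR is defined as the absence of any hyperplastic or cancerous lesion".
- Partial response (PR): "PR is defined as the residual lesion with degeneration and atrophy of endometrial glands".
- No change (NC): "NC is defined as residual lesion without degeneration or atrophy of endometrial glands".
- Progressive disease (PD) is defined relative to the baseline diagnosis: cancer appearing in EAH, or grade 2 or 3 in EC.

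The second primary aspect is "To compare the rate of pregnancy and alive baby delivery", which is not a histology reading.

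**Readers.** For EAH, "the histologic diagnoses of all specimens are made by two categorized pathologists" (Section II.3.1, Comments, item 7). For EC, "histologic diagnoses of all specimens are made by two categorized pathologists" (Section II.3.2, Comments, item 10). Neither item mentions masking, coded specimens, separate readings or what happens when the two readers differ. Section II.4 (Quality Control) covers only changes to the scheme and training. Section III.2 (Random Allocation Method) is silent on masking.

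**Arms.** In EAH without contraindications the arms are "sequential oral medroxyprogesterone acetate (MPA) 500mg QD group; and b) LNG-IUS (Mirena®) group". EC without contraindications adds a third arm, MPA 250 mg plus LNG-IUS. In both contraindication strata the comparison is GnRH-a injection plus LNG-IUS against LNG-IUS alone. No placebo or sham is mentioned. In the device arms "the medical device needs to be replaced by a new one on every hysteroscopy", which is also when tissue is taken.

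**The concern.** A judgement-based outcome needs protection when treatment cannot be hidden from patients and operators. The usual protection is a reader who does not know the arm, and the plan does not ask for one. A team could follow it to the letter and have the primary response read with the arm known.

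The same reading also steers the patient. Under Section II.2.3 and the Comments (item 8 for EAH, item 11 for EC), it decides whether a third cycle is given, whether the patient leaves the trial for hysterectomy, and when fertility treatment begins. A shifted CR call could therefore carry into the timing of the pregnancy and live-birth comparison, although those outcomes are not themselves read from slides.

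Section V states an expectation in one direction: it cites pooled regression in EAH of 90% with LNG-IUS against 69% with oral progestogens.

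**Working it through.** **Step 1: which boundary is exposed.**

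- PR and NC are both residual lesion. They differ only in judged degeneration and atrophy of the glands, with no score or threshold. Section V gives atrophy of the glands as a local effect of the device. The criterion and the expected device effect therefore overlap, which makes this boundary the most exposed. The continuation and withdrawal rules treat PR and NC alike, so an error here changes the reported category but not the patient's course.
- CR against residual lesion depends on whether any lesion is present. It is less exposed but still a reader's call, and it decides the start of fertility treatment.

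**Step 2: where the stated expectation applies.** Section III.1 gives these group sizes:

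| Stratum | Groups × size | Patients | Oral MPA-only arm? |
|---|---|---|---|
| EAH, no contraindication | 2 × 20 | 40 | yes |
| EAH, contraindication | 2 × 14 | 28 | no |
| EC, no contraindication | 3 × 18 | 54 | yes |
| EC, contraindication | 2 × 30 | 60 | no |
| Total | | 182 | |

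The contraindication strata hold 28 + 60 = 88 of 182 patients (48%). Both of their arms carry the device, so an expectation of LNG-IUS over oral progestogen gives no direction of bias there. The same holds for MPA 250 mg plus LNG-IUS against LNG-IUS alone in EC.

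**Step 3: illustration of size.** The plan has no figure for reader error or agreement, so there is none to reproduce. Its 20 per group cannot be rebuilt because no response rates are stated; it is used below only as a scale. Let p be the true CR rate in both arms and q the share of residual lesions read as CR in one arm only. Then

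observed CR = p + q(1 − p).

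With p = 0.69 (the oral EAH figure in Section V), 1 − p = 0.31. The values of q are assumptions. False-positive rates come from exact enumeration of a two-sided, uncorrected chi-square test at 5% with 20 per arm. A p of 0.50 is added to show sensitivity.

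| q | Observed CR, p = 0.69 | False positives | Observed CR, p = 0.50 | False positives |
|---|---|---|---|---|
| 0 | 69.0% | 5.3% | 50% | 4.3% |
| 0.1 | 72.1% | 5.9% | 55% | 5.3% |
| 0.2 | 75.2% | 7.5% | 60% | 8.7% |
| 0.3 | 78.3% | 10.4% | 65% | 15.0% |

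At p = 0.69 the false gain is 3.1, 6.2 or 9.3 points. Against the cited difference of 90 − 69 = 21 points, that is 15%, 30% or 44%. If the other arm's true CRs were also under-called, by 10% or 20% alongside the same q, false positives would be 10.7% or 27.0%; this needs a second assumption.

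**Step 4: how many calls matter.** Start from 14 of 20 CR in each arm. Moving four calls to CR in one arm (18 of 20) gives an uncorrected chi-square p = 0.114. Moving five (19 of 20) gives p = 0.037, or 0.091 by Fisher's exact test. Six (20 of 20) gives 0.008, or 0.020 by Fisher.

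**The case against.** The strongest reply is that silence is not a decision. The documents do not say that the pathologists are unmasked, do not use the term open-label, and do not mention request forms or what they show. A reader might infer that the primary outcome will be read with the arm known; the text does not establish that, and local practice may already be masked. This stands, and it limits the point to what the plan fails to secure.

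A reader might also infer that bias would favour LNG-IUS across the whole trial. Step 2 shows that the documents do not support this.

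The misreading rates have no source in the documents, 69% is an EAH figure while 54 + 60 = 114 of the 182 planned patients have EC, and having two readers is already some safeguard. All of this stands, so the numbers show sensitivity and nothing more.

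Finally, masking has practical limits. A reader given only a study number could not call PD, which depends on the baseline diagnosis. For MPA against LNG-IUS, device-related tissue change may reveal the arm. The documents do not say whether GnRH-a leaves visible changes either. The first limit is met by putting the baseline diagnosis on the form; the others remain.

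What the reply does not remove is that the plan names the readers and the criteria but nothing that keeps arm knowledge away from the call. Anyone using the results could not show from the plan that response was assessed blind.

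**Conclusion.** The point holds in limited form. Treatment is open in practice, the first primary aspect is a qualitative reading, and the plan provides for neither masking, nor independent reading, nor a rule for disagreement. Knowledge of arm could therefore shift response calls, most readily between PR and NC and with more consequence at CR. A direction favouring LNG-IUS can be argued only for the comparisons with oral MPA alone.

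The size of any bias cannot be derived from the documents. Under the assumed 10–30% misreading in one arm and a true CR of 69%, observed CR would be 72–78%, and the false-positive rate at 20 per arm would rise from 5.3% to between 5.9% and 10.4%. These figures use a simple comparison of proportions in place of the survival analysis named in Section III.3, whose event is not specified. They should not be read as an estimate of bias in this trial. The point is a cheap improvement, not evidence that the readings will be biased.

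**What to change.** Add the following to item 7 of the Comments in Section II.3.1 and item 10 in Section II.3.2:

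- Specimens go to the same two pathologists under study number. The form gives the baseline diagnosis (EAH or grade 1 EC, needed to call PD) and describes treatment only as progestogen-based protocol therapy, with no arm or device. That description is true of every arm, since each contains MPA or LNG-IUS.
- Each pathologist reads and records independently before conferring.
- Disagreements are settled by a joint re-read, still masked to arm, ending in one recorded call.
- That reading is the analysed response.

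The two readers are already in the plan, and Section IV already replaces names with numbers. The cost is some relabelling and extra reading time. No dose, visit, group size or clinical rule changes. The remaining weakness is that masking may be incomplete for MPA against LNG-IUS because of device-related tissue changes, and the trial report should say so.

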### 3.2 For Patients Having EC

The treatment schedule for EC is summarized in Figure 2 and Table 2.

**Fig. 2 Study design.** G1, grade 1; EC, endometrial cancer; PgRs, progesterone receptors; CA 125, cancer antigen 125; MRI, magnetic resonance imaging; MPA, medroxyprogesterone acetate; QD, once a day; LNG-IUS, Levonorgestrel-Releasing

intrauterine system, Mirena®; GnRH-a, gonadotropin-releasing hormone agonists, Leuprorelin acetate microspheres; mo, months; CR, complete response; PR, partial response; NC, no change; PD, progressive disease.

**Table 2** The treatment schedule for endometrial cancer (EC)

Visits	1 st	2nd	3rd	4th	5th	6th	7 th	8th	9th	10th	11th	12th
Times (month)	-1	-1/4	0	1	2	3	4	5	6	7	8	9
Procedures	Pre-screening	Screening	Treatment Beginning	The 1st cycle			The 2nd cycle			The 3rd cycle (if necessary)		
History collection	√					√			√			√
Physical examination	√	√	√			√			√			√
Weight	√		√	√	√	√	√	√	√	√	√	√
TCT	√											
MRI	√											
Breast ultrasound	√											
Gynecological ultrasound	√					√			√			√
Endocrine examinations	√											
Liver function test	√			√	√	√	√	√	√	√	√	√
Coagulation function test	√					√			√			√
CA 125	√					√			√			√
CA 199	√					√			√			√
Pathology examinations	√	√				√			√			√
Hysteroscopy		√				√			√			√
Criteria	√	√				√			√			
Informed consent			√									
Random assignment			√									
Medical treatment			√	√	√	√	√	√	√	√	√	√

Response evaluation						√			√			√
Adverse resection				√	√	√	√	√	√	√	√	√
Adverse events			√	√	√	√	√	√	√	√	√	√

**Comments:**

(1) The basic history collection includes detailed history of prior treatment; with or without contraindications of oral highly active progestogens: hypertension, diabetes (DM), liver function damage, thrombotic disease and so on; with or without reproductive endocrine disease: infertility, PCO syndrome, insulin resistance (IR), impaired fasting glucose (IFG) and so on; with or without any other system disease; surgical history, allergy history; family history especially for carcinomas.

(2) If the patient is suspected of having LS, endometrial samples should be taken for pathological immunohistochemistry, and genetic test should be done when necessary.

(3) The basic endocrine examinations include sex hormone, anti mullerian hormone (AMH), and insulin release test (IRT) to rule out PCO syndrome, IR, IFG, and DM. Follow-up treatment will be provided when necessary.

(4) Disease limited to the endometrium (stage 1A) on MRI is confirmed by the designated radiologists.

(5) Laparoscopic multipoint biopsy of ovary and peritoneum when CA 125/199 or imaging examinations are remarkable, so as to rule out ovarian tumor or other metastases.

(6) If the patients has abnormality in breast ultrasound, she needs to visit the Department of Breast Surgery to evaluate the risk of continuous progestogen treatment.

(7) Based on the inclusion and exclusion criteria of this study, patients will be allocated to one of the arms by central randomization with study site

allocation. The arms and interventions and the probability of distribution are as follows:

1) If the patient does not have thromboembolism, liver dysfunction, hypertension, or diabetes, she will be assigned to one of the following three groups, with a probability of 33%, respectively: a) sequential oral medroxyprogesterone acetate (MPA) 500mg QD group; b) sequential oral medroxyprogesterone acetate (MPA) 250mg QD + LNG-IUS (Mirena®) group; and c) LNG-IUS (Mirena®) group;

2) If the patient is diagnosed of thromboembolism, liver dysfunction, hypertension, or diabetes, she will be assigned to one of the following two groups, with a probability of 50%, respectively: a) intramuscular injection of leuprorelin acetate microspheres (GnRH-a) + LNG-IUS group; and b) LNG-IUS (Mirena®) group.

(8) For the groups of oral highly active progestogens, medicine treatment should only be continued if the liver function is normal, which is evaluated by monthly tests.

(9) For the groups of LNG-IUS, the medical device needs to be replaced by a new one on every hysteroscopy to insure adequate drug release

(10) Endometrial tissue sampling for diagnosis should be carried out by hysteroscopy every 3 months, and histologic diagnoses of all specimens are made by two categorized pathologists.

(11) After 6 months' continuous progestogen-based therapy, if the patient has PR/NC, progestogen-based therapy should be continued for one more cycle (3 months), and if the patient still has PR/NC, she will withdraw from this trial and undergo hysterectomy; if the patient has CR at the second or third endometrial evaluation, fertility treatment will be initiated immediately; and if the patient has documented progression on the biopsies at any time, the protocol treatments will be stopped and hysterectomy be recommended.

(12) The option of natural conception or assisted reproduction should be discussed with the fertility specialist in the reproduction center of our hospital; assisted reproduction is recommended if the patient 1) has history of infertility; 2) has risk factors of infertility such as PCO syndrome, obesity, diabetes, and lack of ovulation; or 3) suffers from failed pregnancies after 6 months of natural conception.

(13) If the patient succeeds in conceiving, she will receive professional prenatal examinations from the obstetrics specialist in our hospital.

(14) All the professors in the Department of Obstetrics and Reproductive Center of our hospital are on this research team.

(15) Long-term follow-up will proceed even after treatments are finished, and corresponding clinical treatments will be provided for patients with different conditions.

#### **4. Quality Control:**

(1) Modification of the scheme: If the original scheme is too difficult to implement during the research, it could be revised and confirmed upon discussion by the research group. The modified scheme must be recorded in written form.

(2) Training: Relevant training on researchers will be conducted before the trial starts.

#### **5. Data Entry and Verification:**

Researchers are responsible for on-site data entry and modification. Epidata3.1 epidemiological data entry software will be used for programming by double entries, which include the basic information on the study object and research indicators. When the two independent entries are completed, data consistency will be verified using Epidata3.1. Finally, the verified data will be imported into Excel. Finally, the completed data will be imported into Excel.

### **III. Statistical Analysis Plan**

#### **1. The Sample Size Calculation:**

This clinical study is a RCT and aims to evaluate the fertility-preserving treatments for young women having EAH and EC. Experimental stratification is conducted based on whether the participants have contraindications of oral highly active progesterone (including thromboembolic disease, liver dysfunction, hypertension, and diabetes). The distribution ratio between the experimental group and the control group is 1:1. The estimated sample size can detect difference under  $\alpha = 0.05$  and Power = 0.8, calculating the exact sample size and randomizing grouping. For EC without contraindications of oral highly active progestogens, we will compare sample rates among the three groups by using the PASS software and will calculate the sample size of 18 cases for each group. For EC with contraindications of oral highly active progestogens, we will compare sample rates between the two groups by using the PASS software and will calculate the sample size of 30 cases for each group. Similarly, the calculation of sample size for patients having EAH with and without contraindications of oral highly active progestogens are 14 and 20 cases for each group.

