This RCT will be carried out at West China Second University Hospital between January, 2018 and December, 2020. Based on the inclusion and exclusion criteria of this study, patients with EAH or EC at stage IA and a strong desire to get pregnant will be considered for enrollment. The enrolled patients will be allocated to one of the arms by central randomization. Drugs including the LNG-IUS, oral highly active progestogen (medroxyprogesterone acetate, or MPA), and gonadotropin-releasing hormone agonists (GnRH-a) will be used in this trial. All these drugs were included in not only the abovementioned guidelines but also other guidelines such as ACOG-SGO and JSGO.[13, 14] The objective of this trial is to assess the efficacy of fertility-preserving treatment of EC and EAH in young women using LNG-IUS by analyzing the therapeutic effects, pregnancy rate, and birth rate among different treatment groups.

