#### **3. Statistics:**

SPSS software will be used for statistical analysis. Survival analysis is used for primary end points and chi-square test for secondary end points.

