Clinically, Mirena® LNG-IUS is one of the most widely used Levonorgestrel-releasing intrauterine devices, which is produced by Bayer Health Care Pharmaceutical Inc., Wayne, NY. Mirena®, the progestogen device, has high contraceptive effectiveness. Each Mirena contains 52 mg of levonorgestrel. Its in vivo drug rate during the first five-year period is approximately 20 ug /day and will reduce to 11 ug/day in five years. The hormone released from the IUS causes significant local effect characterized by glandular atrophy and stromal decidualization. This dominant suppressive effect of the endometrium is seen through the overall thickness of the arterial walls with capillary thrombosis. The end result is that the suppression of endometrial tissue growth becomes insensitive to estradiol. The LNG-IUS has an important role in the disease prevention or treatment of uterine pathologies, such as endometrial polyps, endometrial cancer, and tamoxifen-induced changes[18]. Compared with oral progestogens, LNG-IUS can elevate the local drug concentration and act on the PgRs in the endometrium directly, which generates a much higher concentration of progesterone in the endometrial mucosa[17]. LNG-IUS may still be a useful treatment option, especially because it has fewer and milder systemic side-effects such as weight gain and liver damage[6]. Some studies suggest that LNG-IUS is superior to oral progestogens in the fertility-preserving treatment of EAH and EC. Gallos et al[19] reported in a systemic review that LNG-IUS achieved a higher pooled regression rate than oral progestogens for EAH (90 vs 69%,  $P = 0.03$ ).

A higher regression was also seen in a randomized, multicenter study carried out by Orbo et al[20]. This is similar to findings of some studies and systemic reviews[17, 21]

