The use of LNG-IUS alone or in combination with GnRH-a, oral progestogens for fertility-perserving treatment of EC and EAH has been proposed in many guidelines[1, 3, 5, 7, 8, 11]. LNG-IUS was suggested as the first-line medicine treatment for patients having EAH by RCOG-BSGE[1]. In summary, (1) several recent studies have reported encouraging results on fertility-preserving treatment of EC and EAH. (2) Nevertheless, studies focusing on the efficacy and safety of LNG-IUS used alone are still insufficient and weak and based almost exclusively on small studies. (3) In addition, LNG-IUS is used by many only in conjunction with other medicines. Therefore, an appropriately designed RCT is needed urgently to evaluate different fertility-preserving treatments of EAH and EC.

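### EC without contraindications: the plan sizes a three-group comparison but names no contrast, control arm or testing rule, so as written it does not answer the LNG-IUS question

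*Combined protocol and SAP*

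**What the plan says.** Section II.3.2, Comment (7), sets out the arms for EC patients with none of the four listed conditions: "she will be assigned to one of the following three groups, with a probability of 33%, respectively". The arms are MPA 500 mg, MPA 250 mg + LNG-IUS, and LNG-IUS alone. The other three cells (EC with contraindications, and both EAH cells) have two arms each.

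Section III.1 gives alpha 0.05 and power 0.8 and then states: "For EC without contraindications of oral highly active progestogens, we will compare sample rates among the three groups", arriving at 18 per group. It also says "The distribution ratio between the experimental group and the control group is 1:1", without saying which of the three EC arms is the control.

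Section III.3 gives the analysis in one line: "Survival analysis is used for primary end points and chi-square test for secondary end points". It names no pair, reference arm, order of tests or adjustment.

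On purpose, the first primary end point is "To value the efficacies of LNG-IUS as fertility-preserving treatment for early EC and EAH by pathologic response". The introduction says the trial will "assess the efficacy of fertility-preserving treatment of EC and EAH in young women using LNG-IUS", by comparing outcomes between treatment groups. Section V gives as part of the rationale that "studies focusing on the efficacy and safety of LNG-IUS used alone are still insufficient and weak".

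**The concern.** Two of the three arms contain LNG-IUS. A three-group test asks only whether the arms are not all alike, so a significant result can come entirely from the combination. Nothing in the plan then says which pair is examined, at what level, or under what condition.

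Two things are at stake. A significant three-group result could be read as efficacy of LNG-IUS used alone when that arm does no better than MPA 500 mg. And because no rule is written, the pairs and the conditions for testing them could be chosen after the data are seen; one obvious choice, all three pairs at 0.05, inflates the false-positive rate.

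**Working it through.** **Inputs.** From the plan: three arms at 33% each (II.3.2, Comment (7)); alpha 0.05, power 0.8, 18 per group (III.1). The plan does not give sidedness or CR rates for EC; I take two-sided tests and assumed rates. The only rates in the document are in section V, where "LNG-IUS achieved a higher pooled regression rate than oral progestogens for EAH" is reported as 90% vs 69%. These are EAH figures and serve here only as an illustration.

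**The plan's 18.** It cannot be reproduced, because no rates are stated. Working backwards, it fits several different tests:
- Three-group chi-square, 2 df. Power 0.80 needs noncentrality λ = 9.635, so Cohen's w = √(9.635/54) = 0.42. Rates of 40/65/90% give λ = 18 × (0.25² + 0 + 0.25²)/(0.65 × 0.35) = 9.89 and power 0.81.
- One unadjusted pair, 48% vs 90%: n = [1.96√(2 × 0.69 × 0.31) + 0.842√(0.48 × 0.52 + 0.90 × 0.10)]² / 0.42² = 17.8, so 18.
- One pair at 0.05/3, 40% vs 90%: the same formula with 2.394 in place of 1.96 gives 17.6, so 18.

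The number 18 therefore does not reveal which test was intended.

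**Method.** All 19³ outcomes of three Binomial(18, p) arms are enumerated. The statistic is Pearson's, X² = 18 Σ(p̂ᵢ − p̄)² / [p̄(1 − p̄)], against 5.99 for three groups (2 df) and 3.84 for a pair (1 df).

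*One outcome by hand.* LNG-IUS alone 9/18, MPA 500 mg 9/18, combination 16/18: p̄ = 34/54 = 0.630. X² = 18 × (0.0168 + 0.0168 + 0.0672)/0.233 = 7.8, which is significant. For LNG-IUS alone vs MPA, X² = 0.

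**1. Only the combination differs** (probability of rejection)

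| CR: LNG-IUS / MPA / combination | Three-group test | LNG-IUS vs MPA directly |
|---|---|---|
| 50 / 50 / 90 | 0.81 | 0.065 |
| 69 / 69 / 90 | 0.30 | 0.05 |

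**2. No true difference, common CR from 50% to 90%** (probability of any false positive)

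| Rule | Range |
|---|---|
| All three pairs at 0.05, no gate | 0.086–0.156 |
| Pairs at 0.05 only after a significant three-group test | 0.026–0.053 |

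A single Pearson pair at this size has error 0.033–0.065, so the slight excess over 0.05 reflects the small sample rather than multiplicity.

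**3. LNG-IUS better than MPA: power to declare that pair**

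| CR: LNG-IUS / MPA / combination | Three-group and pair both significant | Named contrast, no gate |
|---|---|---|
| 90 / 50 / 70 | 0.67 | 0.785 |
| 90 / 69 / 80 | 0.22 | 0.34 |
| 90 / 69 / 90 | 0.27 | 0.34 |
| 90 / 50 / 90 | 0.76 | 0.785 |

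**Sensitivity to the test.** Section III.3 names survival analysis for primary end points. A log-rank simulation (200,000 replicates; CR seen at months 3, 6 and 9 as in Table 2; no dropout; two assumed timings of response) gave 0.75–0.88 for the three-group test at 50/50/90, an any-false-positive rate of 0.124–0.128 for ungated pairs, and 0.051–0.054 for gated pairs. With continuity-corrected chi-square, ungated pairs gave only 0.007–0.074.

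**The case against.** The strongest reply is that the sentence in III.1 explains how 18 was obtained and is not the analysis plan. Section III.3 neither prescribes a three-group test alone nor excludes pairs. That stands. A reader might infer that the trial is committed to a test that cannot separate LNG-IUS alone from MPA; the documents do not say so. The fault is that nothing is specified.

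Second, LNG-IUS alone vs MPA 500 mg is nowhere declared the single confirmatory question. The introduction and III.1 also speak of evaluating the treatments across groups, and the combination is itself a treatment using LNG-IUS. This stands too: section V supports interest in LNG-IUS alone, but making that contrast primary is the investigators' decision.

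Third, nobody wrote a plan to test three pairs at 0.05. A reader might infer uncontrolled testing; the text does not commit to it. The 0.09–0.16 shows what one unexcluded choice would cost, and it depends on the test and the rates.

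Fourth, the study calls itself phase II, where formal adjustment can be debated. But III.1 claims an alpha and a power, so a formal test is intended and its hypothesis should be identifiable.

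Finally, at 90/50/90 the three-group test rejects with probability 0.84 against 0.785 for the named pair, and a reader might infer that the three-group route is the more powerful. Those are unlike events: rejecting overall is not the same as showing LNG-IUS better than MPA. Like for like, the figures are 0.76 and 0.785.

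**Conclusion.** The omission is real and cheap to correct. For the three-arm EC cell the plan describes one comparison among groups at one alpha and gives no contrast, control arm, order or gate. Taken alone, that comparison does not answer whether LNG-IUS alone differs from MPA 500 mg: under the assumed 50/50/90 it is significant in 81% of trials with no such difference present. If pairs are added, the false-positive rate depends on a gate the plan does not state: 0.03–0.05 with it, 0.09–0.16 without (Pearson).

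All CR rates are assumptions; the qualitative conclusion does not depend on them, but the sizes do.

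Two limits on scope apply. The three-arm problem belongs to this cell only, because the others have two arms. A reader might infer that the other cells, or this one once corrected, are free of multiplicity. They are not: pregnancy and live birth are also primary, and the point made here does not deal with them. Nor does a stated rule repair power: 18 per arm gives 0.34 for 90% vs 69%. The missing rates behind the 18 are a separate matter.

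**What to change.** In III.1 and III.3, for pathologic response in EC without contraindications, state before analysis one of two rules. The same rule should apply whether the test is log-rank or chi-square.

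- **(a) Three-arm closed procedure.** Three-group test at 0.05 first; each pair at 0.05 only if that is significant. With three groups no further split of alpha is needed.
- **(b) One named confirmatory contrast**, two-sided 0.05, not gated. LNG-IUS alone vs MPA 500 mg is the natural candidate, because EAH without contraindications has the same two arms (II.3.1, Comment (4)). The other two pairs are reported as differences with 95% confidence intervals.

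The investigators choose between (a) and (b) and state which of the three arms is control. Under either rule, a significant three-group result should not by itself be reported as efficacy of LNG-IUS alone.

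**Cost.** SAP wording only, if 18 per group is kept. Relative to (b), rule (a) lowers power for LNG-IUS vs MPA by 0.785 − 0.67 = 0.115 at 90/50/70, 0.34 − 0.22 = 0.12 at 90/69/80, 0.34 − 0.27 = 0.07 at 90/69/90, and about 0.03 at 90/50/90. Rule (b) gives up confirmatory claims on the combination.
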